### Methods

#### Study population

This trial will be conducted at the pediatric outpatient clinics of Taipei Hospital, Ministry of Health and Welfare from January 1, 2021, to June 30, 2021. The inclusion criteria are children: (i) aged between 3 and 18 years; (ii) who have access to the smartphone app; (iii) with asthma treatment steps 2–4, requiring regular treatment with controller medication (for at least 6 months over the past year) according to the GINA guidelines; and (iv) who have at least two clinic or emergency department visits related to asthma in the previous year. Children who have comorbidities, or other major medical problems, and who do not have a smartphone or whose caregivers did not have a smartphone were excluded from the study.

#### Protocol

The study enrolls 210 children to detect a 50% reduction in ACT scores, with 80% power and a 20% attrition rate. They will be randomly assigned to an intervention group and a control group. The intervention group download the asthma smartphone app, and follow up monthly via phone calls and clinic visits, while the control group receives reminder calls. At baseline, pediatric allergists examine participants using the International Study of Asthma and Allergies of Childhood (ISAAC) questionnaire. At 3 and 6 months, ACT scores, Mini Pediatric Asthma Quality of Life Questionnaire (MiniPAQLQ), Pediatric Asthma Severity Scores (PASS), Pediatric Asthma Caregiver

Quality of Life Questionnaire (PACQLQ), and peak expiratory flow (PEF) are determined by written informed consent will be obtained from the patients or their guardians. Study protocol approved by the hospital's Institutional Review Board

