### **Smartphone app**

Smartphone self-care app for childhood asthma, based on GINA guidelines, offers personalized support through alerts, information inquiries, data entry, and self-test record reports. Alerts included self-assessment of asthma control, individualized coaching, and air quality information updates. The ACT was used for self-assessments, focusing on shortness of breath, nocturnal symptoms, rescue inhaler use, and daily activities over the last month [16]. Patients were categorized based on ACT scores into green (score > 25), yellow (score 20-24), or red (score < 20). Patients with poor control received education on managing symptoms, trigger avoidance, medication adherence, inhaler technique, peak flow meter usage, and acute symptoms management. The app offers personalized suggestions, advises patients to seek care if control is poor, and assesses situations based on app records.

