### **Statistical analysis**

The study is used an independent t-test to compare baseline demographic data and outcome variables between intervention and control groups. The paired t-test is used to compare

intragroup scores, prescribed treatment courses, PEF changes, and medical costs 6 months before and after the intervention.

The difference-in-difference method is used to assess costs before and at 6 months between intervention and control groups. Significance is set at a two-tailed  $\alpha$  value of .05, and all analyses were conducted using SAS software version 9.1 (SAS Institute, Cary, NC, USA).

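### The only power statement sizes the trial for a halving of ACT scores, which is a worsening on the plan's own bands and does not lead to 210 children

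*SAP*

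**What the plan says.** The sample size is justified in one sentence of the Protocol section: "The study enrolls 210 children to detect a 50% reduction in ACT scores, with 80% power and a 20% attrition rate". The next sentence is "They will be randomly assigned to an intervention group and a control group"; it gives no ratio.

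The Smartphone app section sorts children by ACT score into "green (score > 25), yellow (score 20-24), or red (score < 20" and directs education and advice to seek care to those whose control is poor.

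The Statistical analysis section plans the between-group comparison as follows: "The study is used an independent t-test to compare baseline demographic data and outcome variables between intervention and control groups". The level is .05 ("Significance is set at a two-tailed"). The SAP gives no ACT mean, standard deviation or expected proportion.

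**The concern.** Two things do not fit. First, the effect runs the wrong way: on the plan's bands, a lower ACT score is poorer control, so the sentence describes a trial sized to detect harm from the app. Second, a 50% change in a score whose yellow band covers only 20 to 24 is very large. A trial seeking it would need a few dozen children at most, not 210.

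This sentence is the only power claim in the document, and ACT is the only outcome tied to the sample size. If the effect is misdescribed, a reader cannot tell which difference the 80% refers to, and an inconclusive ACT result would be hard to interpret.

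**Working it through.** **Inputs from the SAP.** 210 enrolled, 80% power and 20% attrition (Protocol); two-tailed .05 and an independent t-test (Statistical analysis).

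**Inputs assumed, because the SAP gives none.** 1:1 allocation, with 2:1 as a check; baseline ACT mean 16 to 22; SD 3 to 6, with SD 10 as an extreme.

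**Direction.** No assumption is needed. Halving a yellow-band score of 20 to 24 gives 10 to 12, which is in the red band.

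**Evaluable children.** 210 × 0.8 = 168, or 84 per arm at 1:1.

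**Method.** Power of the two-sample t-test from the noncentral t distribution, with d = difference / SD, noncentrality d × √(n₁n₂/(n₁+n₂)) and n₁+n₂−2 degrees of freedom. The number to enrol is the evaluable total divided by 0.8.

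**Attempt to reproduce 210 from a halved mean** (difference = baseline / 2):

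| Baseline | SD | d | n per arm | Total to enrol |
|---|---|---|---|---|
| 22 | 3 | 11/3 = 3.67 | 3 | 6/0.8 = 7.5, so 8 |
| 22 | 6 | 11/6 = 1.83 | 6 | 12/0.8 = 15 |
| 16 | 3 | 8/3 = 2.67 | 4 | 8/0.8 = 10 |
| 16 | 6 | 8/6 = 1.33 | 10 | 20/0.8 = 25 |
| 16 | 10 | 8/10 = 0.80 | 26 | 52/0.8 = 65 |

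At 2:1 the corresponding totals are 8 to 30, and 75 at SD 10. A 50% rise is the same number of points, so correcting the direction alone leaves these figures unchanged. With 84 per arm, power for a halved mean exceeds 99.9% even at baseline 16 and SD 10.

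**SD at which a halved mean would need 84 per arm.** The detectable d at 84 per arm is 0.435, so SD = 8/0.435 = 18.4 (baseline 16) to 11/0.435 = 25.3 (baseline 22). Neither is credible on a scale with cut-points at 20 and 25.

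**Attempt to reproduce 210 from 0.5 SD.** At 1:1, 64 per arm, 128/0.8 = 160. At 2:1, 96 + 48 = 144, 144/0.8 = 180. With 168 evaluable, power for 0.5 SD is 89.6% at 1:1 and 85.9% at 2:1, not 80%. At 90% power, 86 per arm are needed, 172/0.8 = 215: close to 210, but not at the stated power.

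**What 210 does give at 80% power.**

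| Evaluable | Detectable difference |
|---|---|
| 84 / 84 (1:1, 20% loss) | 0.435 SD |
| 112 / 56 (2:1, 20% loss) | 0.461 SD |
| 105 / 105 (1:1, no loss) | 0.388 SD |

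At 84 per arm this is 0.435 × 3 = 1.3 points to 0.435 × 6 = 2.6 points for an SD of 3 to 6.

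**The case against.** The strongest reply is that the size mismatch depends on how the sentence is read. The SAP does not say that the sample size was calculated with the t-test. Its ACT bands suggest another reading: a halved proportion of poorly controlled children, which would also explain the word reduction. With pooled variance, no continuity correction, 1:1 and 20% attrition, 40% falling to 20% needs 82 per arm, 164/0.8 = 205, and a control proportion of about 39% matches 84 per arm. However, 50% falling to 25% needs 145 and 30% falling to 15% needs 303, so the match depends on one particular proportion.

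Likewise, 0.5 SD at 3:1 allocation comes to 210 by the normal approximation. By the t-test, 126 against 42 evaluable children have 79.7% power, and 215 must be enrolled to reach 80%.

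It is also fair that the mean, SD and ratio behind a sample size are often left to a protocol, so their absence here is no fault in itself.

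What stands: it cannot be said that no reading yields 210, and 210 is not shown to be wrong. What does not stand: none of these inputs is in the document, and the proportion reading would need a between-group comparison of proportions that the Statistical analysis section does not plan. None of this touches the direction, which contradicts the bands without any assumption.

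**Conclusion.** The concern holds. The effect named in the power statement is a worsening on the SAP's own bands. Under the planned t-test at 80% power and 1:1 allocation, neither a halved mean nor 0.5 SD leads to 210. The halved-mean range rests on the assumed means and SDs, but the gap survives wide variation in them: 65 at SD 10 with 1:1 allocation, and 75 with 2:1. The 0.5 SD figure needs no mean or SD, only the allocation ratio.

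The consequence is limited. The trial is not underpowered for the effect as literally written, and no estimate or participant number depends on the sentence. It should be fixed because it is the document's sole power claim and, as it stands, does not identify the difference the trial can detect.

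**What to change.** Keep 210.

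1. The sponsor states the effect that was assumed: endpoint, direction, units, SD or control proportion, and allocation ratio.
2. Reword the effect so that it matches that answer and the direction of the ACT bands.
3. If the planned t-test on ACT score was the basis, a suitable sentence would be: *Assuming 1:1 allocation and 20% attrition (84 evaluable per arm), 210 children give 80% power at two-sided .05 for a between-group difference of about 0.43 SD in ACT score, higher being better.* Add the difference in points from the sponsor's SD, and recompute if allocation is not 1:1. This figure is worked back from 210, so it needs the sponsor's confirmation.
4. If 0.5 SD was meant, correct the power to about 90% (at 1:1).
5. If a halved proportion of uncontrolled children was meant, state the control proportion and add the matching between-group comparison to the Statistical analysis section.

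The cost is one answer from the sponsor and one reworded sentence, plus one added analysis in the last case. Sample size, arms and the tests already planned stay as they are.

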### **Smartphone app**

Smartphone self-care app for childhood asthma, based on GINA guidelines, offers personalized support through alerts, information inquiries, data entry, and self-test record reports. Alerts included self-assessment of asthma control, individualized coaching, and air quality information updates. The ACT was used for self-assessments, focusing on shortness of breath, nocturnal symptoms, rescue inhaler use, and daily activities over the last month [16]. Patients were categorized based on ACT scores into green (score > 25), yellow (score 20-24), or red (score < 20). Patients with poor control received education on managing symptoms, trigger avoidance, medication adherence, inhaler technique, peak flow meter usage, and acute symptoms management. The app offers personalized suggestions, advises patients to seek care if control is poor, and assesses situations based on app records.

### **Outcome measures**

The physician diagnoses asthma at Taipei Hospital; National Health Insurance Program retracted sociodemographic data. A retrospective chart review is used to assess the use of prescribed systemic corticosteroids (prednisolone), maintenance inhaler treatment (salmeterol/fluticasone [Seretide™, GSK Group of Companies], and anti-leukotriene treatment (montelukast). Six months before and after using the app, direct (unscheduled visits to the emergency department and hospitalization costs) and indirect costs (days off work by parents to care for their children and transportation costs) are measured, and transportation costs were estimated using a national website.

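### Direct cost covers only emergency and hospital care, so the planned cost comparison cannot tell a net saving from care moved to the clinic

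*SAP*

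**What the plan says.** The SAP, Outcome measures, measures costs over six months before and six months after app use. Direct cost is "direct (unscheduled visits to the emergency department and hospitalization costs". Indirect cost is parents' lost workdays plus travel. Neither list contains clinic visits, calls, the app or medication. Drug use is collected ("A retrospective chart review is used to assess the use of prescribed systemic corticosteroids (prednisolone", together with the maintenance inhaler and montelukast), but it is not listed as a cost.

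Under Protocol, the intervention group downloads the app, and the arms then differ in contact: "follow up monthly via phone calls and clinic visits, while the control group receives reminder calls". Under Smartphone app, the app also "advises patients to seek care if control is poor".

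Under Statistical analysis, a paired t-test compares "medical costs 6 months before and after the intervention", and a difference-in-difference compares *costs* between the groups. Neither label is tied to the items listed under Outcome measures.

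**The concern.** The intervention works partly through outpatient contact: scheduled monthly follow-up, and advice to seek care when control is poor. The direct-cost definition counts the events this contact may avert but not the contact itself. An emergency visit replaced by a clinic visit is scored as a full saving, with the replacement priced at zero. Subtracting the baseline period does not help, because that removes stable differences between the arms and not a resource introduced in one arm after baseline.

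A fall in emergency and hospital cost would be a real fall in that quantity. Under the labels *direct*, *medical costs* or *costs*, however, it is easily read as a saving in care overall. The analysis as defined could not tell such a saving from a change in where care is given.

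**Working it through.** The SAP states no cost figure, so there is none to reproduce. The check compares the cost definition with the design and then writes out what is left out.

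**1. Resources against cost items (SAP, Protocol, Smartphone app and Outcome measures)**

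| Resource | Intervention | Control | In direct cost? |
|---|---|---|---|
| Emergency visits, hospitalisation | yes | yes | yes |
| Monthly clinic follow-up | yes, share of contacts not given | not described | no |
| Calls | yes | reminder calls, frequency not given | no |
| App | yes | not described | no |
| Clinic visits prompted by the app | possible | not applicable | no |
| Asthma drugs | use abstracted | use abstracted | no |

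**2. Formula.** For any cost item, D = (intervention after - intervention before) - (control after - control before), per child. Then

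D(fuller direct cost) = D(emergency + hospital) + k × c + D(calls) + D(app) + D(drugs),

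where k is D for the number of clinic visits and c is the cost of one clinic visit. The planned analysis keeps only the first term. The terms for visits, calls and drugs can each be negative.

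**3. What the SAP says about k.** It does not fix k. Two statements reduce the expected contrast between the arms. The outcome assessments ("At 3 and 6 months, ACT scores, Mini Pediatric Asthma Quality of Life Questionnaire (MiniPAQLQ), Pediatric Asthma Severity Scores (PASS" and others) are not restricted to one arm, although their setting is not stated. All children enter as "requiring regular treatment with controller medication", so some clinic contact in both arms is likely.

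**4. Illustration (all counts assumed).** Take 2 clinic visits per child in each arm in the six months before. In the first three rows controls make 2 after, for example the two assessments if held in the clinic. Let r be the cost of a clinic visit divided by that of an emergency visit, assumed to be 0.1 to 0.5.

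| Intervention after | Control after | k | k × r, emergency-visit equivalents per child |
|---|---|---|---|
| 2 (months 3 and 6 only) | 2 | (2-2)-(2-2) = 0 | 0 |
| 4 | 2 | (4-2)-(2-2) = 2 | 0.2 to 1.0 |
| 6 (every month) | 2 | (6-2)-(2-2) = 4 | 0.4 to 2.0 |
| 3 | 4 | (3-2)-(4-2) = -1 | -0.5 to -0.1 |

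Visits prompted by the app would add to the intervention counts. Whether a visit is classed as care or as trial assessment also moves k.

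**5. Scale.** The entry criterion is children "who have at least two clinic or emergency department visits related to asthma in the previous year". That minimum is 2 per 12 months, or 1 clinic or emergency visit per six months. Against that scale the illustrated values can be negligible or large.

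**6. Can another planned outcome fill the gap?** Only partly. Travel cost and lost workdays may rise if clinic trips rise. The SAP does not say which trips or absences count, and neither measure yields visit counts or visit cost.

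**The case against.** The strongest reply is that the SAP never announces an overall saving. It sets no net-cost or cost-effectiveness objective, it lists the components in the same sentence as the term, and it measures the events the app is meant to prevent. Programme costing and perspective could be in a protocol that is not at hand. The trial is sized on the ACT score, and nothing marks cost as primary.

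Much of this stands. The SAP makes no overall claim, and the narrower outcome is legitimate. The definition itself is stated, though, so it is not a detail left to the protocol. The labels under Statistical analysis are wider than the items measured, and nothing confines the conclusion to them.

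A reader might infer that the plan necessarily overstates the saving, by as much as six clinic visits per child. The SAP does not support that. Monthly contact mixes calls with visits in unknown proportion, control clinic visits are neither excluded nor counted, controls also receive calls, and the direction of the drug term is unknown. It would also go too far to say that no outcome bears on a shift of care, since travel and lost workdays give a partial signal.

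A last objection is that costing every clinic visit would charge trial assessments as care. That is fair, and the fix separates them.

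**Conclusion.** The point holds as a mismatch between a stated cost definition and the design. The direct-cost comparison omits outpatient care and programme resources that the design may add to one arm after baseline, so it cannot distinguish a net direct-cost saving from care moved to the clinic.

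Size and sign are not derivable. The illustrated clinic-visit term, -0.5 to 2.0 emergency-visit equivalents per child, includes zero and rests wholly on assumed visit counts and an assumed price ratio. It shows that the omission could matter, not that it does. A tilt towards the app arm is plausible, but its clinic-visit part disappears or reverses if control clinic visits rise as much as or more than those in the app arm. The point limits what may be concluded about cost and does not affect the clinical outcomes.

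**What to change.** **Preferred.** In both arms and both six-month windows:

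- count asthma-related clinic visits from the charts, including the monthly follow-up, and report the counts by arm and window;
- include in direct cost the cost of these visits and of the drugs already abstracted, plus a simple estimate of call and app cost;
- list visits held only for trial assessment separately;
- keep emergency plus hospitalisation cost as a labelled component;
- state under Statistical analysis which items *medical costs* and *costs* contain.

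**If these items cannot be obtained.** Name the outcome emergency and hospitalisation cost under both Outcome measures and Statistical analysis, state what the two labels contain, and draw no conclusion about overall direct or medical cost.

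**Cost.** The preferred change needs modest extra abstraction, because chart review is described only for drug use, and it needs unit prices for visits and drugs. Visits at other hospitals may be missed, and the apparent saving may shrink. The lighter change needs no new data but gives up any overall saving claim.

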### **Statistical analysis**

The study is used an independent t-test to compare baseline demographic data and outcome variables between intervention and control groups. The paired t-test is used to compare

intragroup scores, prescribed treatment courses, PEF changes, and medical costs 6 months before and after the intervention.

The difference-in-difference method is used to assess costs before and at 6 months between intervention and control groups. Significance is set at a two-tailed  $\alpha$  value of .05, and all analyses were conducted using SAS software version 9.1 (SAS Institute, Cary, NC, USA).

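### Non-cost outcomes are compared between randomised arms by an unadjusted t-test, although age and GINA step are known at entry and could be adjusted for at almost no cost

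*SAP*

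**What the plan says.** All of this is in the SAP.

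- **Allocation** (Protocol section): "They will be randomly assigned to an intervention group and a control group". No ratio and no stratification are stated.
- **Known at entry** (Study population section): children are "aged between 3 and 18 years" and "with asthma treatment steps 2–4, requiring regular treatment with controller medication". Both items must be established before a child can be enrolled. They appear only as eligibility criteria.
- **Between-arm analysis** (Statistical analysis section): an "independent t-test to compare baseline demographic data and outcome variables between intervention and control groups". One unadjusted test thus serves both baseline description and outcome comparison.
- **Costs** (same section): "The difference-in-difference method is used to assess costs before and at 6 months between intervention and control groups". This uses the prior cost but names no other covariate.
- **Within-arm analysis** (same section): paired t-tests, which do not compare the arms.

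**The concern.** The plan admits children across 15 years of age and three treatment steps, and then compares the arms as if nothing were known about them. Age and step are plausibly related to symptom scores, treatment courses and PEF. Two things follow for the non-cost outcomes. Variation that these factors could explain stays in the error term, so intervals are wider than they need to be. And if randomisation happens to leave one arm older or on higher steps, the planned analysis has no means of allowing for it. Any adjustment would then have to be devised after the data are seen.

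A smaller matter is the t-test on baseline demographics. Under random allocation the null hypothesis of that test is true by design. A small p-value can only be chance, and a large one does not show that a prognostic factor is balanced.

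**Working it through.** **Inputs from the SAP.** 210 children enrolled, 20% attrition, 80% power, two-sided alpha .05. Evaluable: 210 × 0.8 = 168, or 84 per arm if allocation is 1:1 (assumed).

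**The plan's own figure.** The 210 cannot be reproduced, because the target ("The study enrolls 210 children to detect a 50% reduction in ACT scores, with 80% power and a 20% attrition rate") comes without a standard deviation, baseline mean or event rate. The point does not depend on it. The calculation below takes 80% power at 84 per arm as given.

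**Step 1: effect implied by 80% power.** (1.960 + 0.842) × √(2/84) = 0.432 standard deviations (normal approximation).

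**Step 2: effect of adjustment.** If age and step together explain a share R² of the outcome variance within arms, the standard error is multiplied by √(1 − R²). Power becomes Φ(2.802/√(1 − R²) − 1.960). The sample that would match the precision of 210 unadjusted is 210 × (1 − R²). The SAP gives no R², so a range is shown.

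| R² (assumed) | SE multiplier | Fall in SE | Power at 84 per arm | Equivalent of 210 |
|---|---|---|---|---|
| 0.02 | 0.990 | 1.0% | 80.8% | 206 |
| 0.05 | 0.975 | 2.5% | 82.0% | about 200 |
| 0.10 | 0.949 | 5.1% | 84.0% | 189 |
| 0.20 | 0.894 | 10.6% | 87.9% | 168 |

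The table leaves out the small price of estimating the coefficients. Age (one term) and step (two indicators) cost roughly 3/168 = 1.8% in variance. At R² = 0.02 the net variance factor is about 0.98 × 1.018 = 0.998, which is break-even. From 5% upwards there is a net gain.

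**Step 3: chance imbalance.** Suppose a covariate has correlation ρ with the outcome and is imbalanced by z standard errors. With no treatment effect, the unadjusted statistic is then approximately normal with mean ρz and variance 1 − ρ². At z = 1.96 the chance of a two-sided p < .05 is:

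- ρ = 0.2: 6.3%
- ρ = 0.3: 7.9%
- ρ = 0.5: 12.9%

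At z = 1 and ρ = 0.3 it is 5.0%, so the problem is confined to the larger imbalances. An imbalance of |z| ≥ 1.96 occurs in 5% of randomisations for any one covariate.

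**Step 4: baseline p-values (secondary).** With k independent baseline variables, the chance of at least one p < .05 under correct randomisation is 1 − 0.95^k:

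- k = 5: 22.6%
- k = 10: 40.1%
- k = 15: 53.7%

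The SAP neither lists nor counts the variables, so k is an assumption. Correlation among them would alter the figures.

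**The case against.** **The planned test is not wrong.** This stands. Averaged over randomisations, the unadjusted t-test keeps its type I error. A reader might infer from Step 3 that the trial's false-positive rate is inflated. It is not: those figures are conditional on a large imbalance having occurred, and other randomisations offset them.

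**Costs are already handled differently.** This also stands. A reader might infer that every between-arm interval is too wide by the amounts in the table. The difference-in-difference analysis subtracts each child's prior cost, and with it any stable effect of age or step. Only a relation between these factors and the change in cost could add precision, so the √(1 − R²) gain does not carry over.

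**The size is not in the document.** True. R² and the number of baseline variables are both assumed. At the low end the gain is negligible, and quoting only the favourable end would mislead.

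**No harm from baseline p-values is stated.** The SAP says that baseline data are compared. It does not tie a p-value to an adjustment, to a declaration of balance or to the discounting of a result. Dropping these tests changes no treatment estimate.

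**The wording is open.** The phrase about outcome variables could be read as meaning their baseline values only. On that reading the SAP names no between-arm test at all for non-cost outcomes, and the model proposed below would fill the gap.

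What remains after these objections is that covariates certain to be available are not used where they could help, and that using them costs little.

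**Conclusion.** The point holds as an optional improvement in efficiency and in the handling of chance imbalance, limited to the non-cost outcomes. Assuming 1:1 allocation, 84 evaluable children per arm and 80% power unadjusted, the gain runs from nothing worth having (R² of 2%) through 2 and 4 power points (5% and 10%) to about 8 (20%). Which of these applies cannot be settled from the SAP. The document does not support the view that the planned t-test is invalid, that the cost comparison suffers the same loss, or that baseline p-values will steer the analysis. The baseline tests are uninformative, and removing them is a matter of reporting.

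**What to change.** 1. Analyse each non-cost between-arm comparison with a prespecified linear model containing arm, age, GINA step at entry (2, 3, 4) and, where measured, the baseline value of the outcome. Use these covariates whatever balance is observed.
2. State for which outcomes a baseline value exists. The Protocol section lists ACT, MiniPAQLQ, PASS, PACQLQ and PEF at 3 and 6 months only, whereas the paired tests in the Statistical analysis section imply an earlier value. The baseline value is often the most useful covariate.
3. Keep the difference-in-difference analysis for costs. Age and step may be added to it.
4. Show baseline data as mean (SD) or n (%) by arm, without p-values.

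The cost is a change of SAP wording. Age and step need no new data, because eligibility already requires them. The models carry three covariate terms, or four with a baseline value, among about 168 evaluable children. With intercept and arm, the larger model leaves 168 − 6 = 162 residual degrees of freedom, against 166 for the t-test.

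### With 20% attrition expected, the between-arm t-test on scores and PEF is by default a completer analysis at 6 months; a baseline-adjusted repeated-measures model should replace it

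*SAP*

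**What the plan says.** The SAP's Protocol section fixes the size and the expected loss: "The study enrolls 210 children to detect a 50% reduction in ACT scores, with 80% power and a 20% attrition rate". On allocation it says: "They will be randomly assigned to an intervention group and a control group". Scores are taken twice after baseline: "At 3 and 6 months, ACT scores, Mini Pediatric Asthma Quality of Life Questionnaire (MiniPAQLQ), Pediatric Asthma Severity Scores (PASS), Pediatric Asthma Caregiver" (the list goes on to the caregiver quality-of-life score and PEF).

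The Statistical analysis section names three methods:

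- Between arms, an "independent t-test to compare baseline demographic data and outcome variables between intervention and control groups".
- Within arms, a paired t-test for "intragroup scores, prescribed treatment courses, PEF changes, and medical costs 6 months before and after the intervention".
- For costs only: "The difference-in-difference method is used to assess costs before and at 6 months between intervention and control groups".

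The section ties the between-arm t-test to no visit. It names no analysis set, no method for missing scores and no model that joins the 3- and 6-month visits. It also does not write down a complete-case rule.

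**The concern.** A two-sample t-test on 6-month scores needs a 6-month score from each child it includes. Unless values are imputed, and the SAP names no imputation, the children the plan itself expects to lose leave that comparison. Whatever they contributed at baseline or 3 months has no influence on it. Nor does the test use the baseline score to sharpen the comparison among those who remain.

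The harm is mainly bias, not power, because attrition is already among the sample-size inputs. Follow-up contact differs by design: the app arm has the app, monthly calls and clinic visits, and the control arm has reminder calls. Which children stay, and how that depends on their asthma control, could therefore differ between arms. If it does, the 6-month difference among completers is not the difference between the groups as randomised, and the t-test's 5% error rate no longer holds.

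**Working it through.** **Inputs from the SAP.** 210 children, 20% attrition, two randomised arms, visits at 3 and 6 months, two-sided 5% level. The allocation ratio is not given; 1:1 (105 per arm) is assumed. Loss by arm, and the score gap between lost and retained children, are not given and are assumed below.

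**The plan's own figure.** The 210 cannot be reproduced, because no SD, mean or event rate is stated. Nothing below depends on how it was derived.

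**Number affected.** 210 × 0.20 = 42 children without a 6-month score; 210 − 42 = 168 remain, or 84 per arm. For scale, 84 per arm has 80% power for (1.96 + 0.842) × √(2/84) = 0.43 SD.

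**Bias of a completer comparison.** Suppose a fraction p of an arm is lost and the lost children are worse than the retained by g (in SD). The whole-arm mean is then the retained mean minus p × g, so the completer mean is too favourable by p × g. The bias in the arm difference is

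p(app) × g(app) − p(control) × g(control),

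which with a common gap is [p(app) − p(control)] × g. With no true effect and 105 × (1 − p) children per arm, SE = √(1/n₁ + 1/n₂) and type I error = Φ(−1.96 + b/SE) + Φ(−1.96 − b/SE).

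| Assumed loss (mean 20%) | n per arm | SE | Gap g | Bias b | b/SE | Type I error |
|---|---|---|---|---|---|---|
| 25% vs 15% | 78.75, 89.25 | 0.155 | 0.5 | 0.10 × 0.5 = 0.05 | 0.32 | 0.062 |
| 25% vs 15% | 78.75, 89.25 | 0.155 | 0.8 | 0.10 × 0.8 = 0.08 | 0.52 | 0.081 |
| 30% vs 10% | 73.5, 94.5 | 0.156 | 0.5 | 0.20 × 0.5 = 0.10 | 0.64 | 0.099 |
| 30% vs 10% | 73.5, 94.5 | 0.156 | 0.8 | 0.20 × 0.8 = 0.16 | 1.03 | 0.177 |

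The arm with the larger loss looks better than it is. Swapping the arms reverses the sign of b and leaves the type I error unchanged.

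**Boundary cases of the same formula.**

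- Random loss (g = 0): no bias, even at 30% versus 10%.
- Equal 20% loss with the same gap in both arms: 0.20 × g − 0.20 × g = 0.
- Equal 20% loss with a gap of 0.5 in one arm and 0 in the other: 0.20 × 0.5 = 0.10 SD.

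**Does using the earlier scores help?** A simulation assumed 105 per arm, 1,500 runs, no true effect, correlation 0.3 to 0.7 between baseline, 3 and 6 months, and all loss after month 3. It compared the t-test on observed 6-month scores with a likelihood-type estimate that also uses the baseline and 3-month scores. Monte Carlo error of a bias is about 0.155/√1500 = 0.004 SD.

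| Loss | How loss arises | Bias, t-test | Type I error, t-test | Bias using earlier scores (absolute) |
|---|---|---|---|---|
| 30% vs 10% | random | 0.001 to 0.011 | 0.046 to 0.060 | at most 0.011 |
| 30% vs 10% | low 3-month score doubles the odds, both arms | 0.034 to 0.085 | 0.051 to 0.093 | at most 0.002 |
| 20% vs 20% | odds ratio 3 in one arm, random in the other | 0.058 to 0.135 | 0.069 to 0.141 | at most 0.004 |
| 30% vs 10% | odds ratio 3 in the arm losing 30%, random in the other | 0.081 to 0.189 | 0.078 to 0.227 | at most 0.003 |

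Where loss depends on a score already observed, using that score removes the bias. The simulation does not cover loss before month 3 or loss driven by unseen 6-month values.

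**The case against.** The strongest reply is that much of this is read from silence. The SAP states no complete-case rule, and a t-test can be run on imputed data. It gives no visit, so a separate 3-month t-test is compatible with the text. This stands to the following extent: a reader might infer that the plan discards a fifth of the children and ignores all 3-month data, but the document does not say so. What can be said is limited to the 6-month comparison, and to what a t-test does by default when no imputation is specified.

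Three further objections also hold:

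- **Direction.** A reader might infer that the completer analysis favours the app. Nothing in the SAP supports that. Closer contact would ordinarily favour retention in the app arm, and the bias would then run against it.
- **Unequal loss.** A reader might infer that different loss by arm is enough to break the randomised comparison, or that the t-test is valid only when loss is unrelated to outcome. Neither is right. Random loss of 30% versus 10% gives no bias, and outcome-related loss that is the same in both arms cancels when there is no true effect. Equal totals do not reassure either, as the 20% versus 20% case shows.
- **Scope.** On medication the SAP says: "A retrospective chart review is used to assess the use of prescribed systemic corticosteroids". Such data may survive a missed questionnaire, and costs have their own analysis. Neither need lose 42 children.

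Finally, a mixed model is no complete cure. It corrects only for loss that depends on observed scores, and the SAP does not say how many of the 42 would reach month 3. The Protocol section also names only the ISAAC questionnaire at baseline, so a baseline value of each score is implied by the paired tests rather than listed. These limits shape the remedy but do not remove the defect.

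**Conclusion.** The concern holds for ACT, MiniPAQLQ, PASS, PACQLQ and PEF at 6 months. The stated between-arm method is by default a completer analysis that leaves out about 42 of 210 children, does not use their earlier scores and does not adjust for baseline. It is biased if loss relates to outcome differently by arm, or relates to outcome and differs in amount by arm.

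Under the assumed losses and gaps in the first table, the bias is 0.05 to 0.16 SD in either direction, against the 0.43 SD that 168 children could detect with 80% power. Type I error is 6% to 18%. The loss rates by arm, the gaps and the 1:1 allocation are all assumptions; only the overall 20% is the plan's. With random loss there is no bias.

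The criticism is of the method stated, which a better one can replace using scores already planned. It does not rest on the lack of a written missing-data policy, which a separate protocol may supply. The change should be made before the data are analysed; confidence is medium, because the pattern of loss is unknown.

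**What to change.** For the five outcomes, replace the between-arm t-test with a linear mixed model for repeated measures:

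- Include all randomised children in their assigned arm.
- Fit baseline value, arm, visit and arm-by-visit to the 3- and 6-month scores, with scores from the same child allowed to correlate.
- Report the 6-month arm contrast, with its confidence interval, as the estimate.
- State that each score is recorded at baseline, as the paired tests imply. A child with a baseline score only adds nothing if baseline is a covariate. Entering baseline as a first response with a common mean across arms keeps that child in the model.

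Add one sensitivity analysis that shifts missing 6-month values by an amount stated in advance, applied to each arm in turn. Its effect is easy to read: with 20% missing, a shift of 0.5 SD in one arm moves the contrast by 0.20 × 0.5 = 0.10 SD.

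The chart-review medication outcomes and the cost analysis need no change on this account. The cost is new SAP wording and slightly more analysis work with a standard procedure in the software already named. No new data are needed, provided the baseline scores are collected.
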